3.4.1 Primary Efficacy Endpoints

Primary Analysis

The primary PD endpoint is the difference in the percent change in hs-CRP levels from Baseline (average of all hs-CRP values prior to the administration of study drug) to the End of Treatment (average of Week 10 and Week 12) between each active group and placebo.

The Hodges-Lehmann estimate for median of differences for each active group vs. placebo along with the 95% confidence intervals will be presented. P-value from the Wilcoxon test will also be presented. The nonparametric analysis will account for the covariate CKD Stage (3 vs. 4 and 5) by aligning responses within the strata defined by the covariate prior to analysis. Median and quartiles will also be presented for hs-CRP values at baseline, end of treatment, and percent change in hs-CRP from baseline to End of Treatment.

The sample SAS code for Hodges-Lehmann estimates for each treatment arm vs. Placebo can be found below:

.....

*Note: PCHG = Percent change in hs-CRP from baseline to End of Treatment (average of values at Week 10 and Week 12).

* CKD = CKD Stage (stage 3 vs. stage 4 and 5)

* TRT = Treatment group

* VISIT = Study Visit

*****;

```
proc npar1way data=efficacy (where=(TRT in (1, #) & VISIT = "End of Treatment")
    wilcoxon hl(refclass="1") alpha=.05 align=strata(hl);
    class TRT;
    strata CKD;
    var PCHG;
    ods output WilcoxonScores=WilcoxonScores HodgesLehmann=HodgesLehmann;
    output out=pvalue;
```

run;

The overall familywise error rate will be controlled at $\alpha = 0.05$ using the sequential testing procedure for the primary efficacy endpoint comparing the 2 dose levels of Ziltivekimab vs placebo. The high dose (30 mg) will be compared with placebo first. If the high dose is significant, then the low dose (15 mg) will be compared with placebo. The procedure will stop whenever a nonsignificant test occurs.

Sensitivity Analyses

Sensitivity analyses will be performed as follows:

- (1) The nonparametric analysis method used to analyze the primary efficacy endpoint will be performed on the PP population.
- (2) Analysis of hs-CRP on a log scale will be performed using MMRM on the ITT population. MMRM analysis will be carried out which includes log of ratio to baseline as the response variable, variable for CKD stage (3 vs. 4 and 5), treatment group, visit and treatment group-by-visit interaction as categorical fixed effects, and log of baseline-by-visit interaction as a covariate. The mixed model will include analysis visits at Week 2, Week 4, Week 10, and Week 12. This model will be analyzed to present estimates for ratio to baseline (with 95% confidence intervals), treatment ratio estimates (with 95% confidence intervals) for each active group to placebo with p-values. Estimates and 95% confidence intervals will also be presented on a percentage scale.

An unstructured covariance matrix will be used to model the within-subject correlation. The Kenward-Roger approximation will be used to adjust the denominator degrees of freedom. The analysis will be performed based on all observed post-baseline visits without any imputation of missing data. In the case when the mixed model for repeated measures (MMRM) fails to converge using an unstructured covariance matrix in any stage, a less stringent covariance matrix (e.g., autoregressive 1) will be used. The mean values from Week 10 and Week 12 as well as the treatment difference of average will be estimated using the LMSESTIMATE statement within PROC MIXED for mixed models. The sample SAS code is provided below:

*Note: PCHG = Percent change in hs-CRP from baseline at each visit

* CKD = CKD Stage (stage 3 vs. stage 4 and 5)

* TRT = Treatment group

* VISIT = Study Visit

```
* LOG_R2BASE = Log of ratio to Baseline
* LOG_BASE= Log of baseline
*****;

proc mixed data=crp (where=(LOG_R2BASE ne . and
  VISIT in ("VISIT 2 (WEEK 1)", "VISIT 3 (WEEK 2)",
  "VISIT 5 (WEEK 4)", "VISIT 8 (WEEK 10)", "VISIT 9 (WEEK 12)"))
  method=reml covtest ;
  class USUBJID CKD TRT VISIT;
  model LOG_R2BASE = CKD TRT VISIT TRT*VISIT LOG_BASE*VISIT /
  ddfm=KR residual;
  repeated VISIT / type=un subject=USUBJID ;
  lsmeans TRT*VISIT / cl;
  lsestimate TRT*VISIT
/*average estimates*/
"Placebo avg week 10, 12" [0.5 1 4] [0.5 1 5],
"15 mg avg week 10, 12" [0.5 2 4] [0.5 2 5],
"30 mg avg week 10, 12" [0.5 3 4] [0.5 3 5],
/*differences in averages*/
"15 mg-placebo week 9, 13 avg" [0.5 2 4] [0.5 2 5] [-0.5 1 4] [-0.5 1 5],
"30 mg-placebo week 9, 13 avg" [0.5 3 4] [0.5 3 5] [-0.5 1 4] [-0.5 1 5]/CL;
ods output LSMEstimates = LSMEstimates LSMeans = LSMeans;
run;
```

- (3) Sensitivity analysis will be performed on the ITT population using a pattern-mixture model using sequential modeling with multiple imputation on the log transformed hs-CRP data. Subjects in the active groups who terminated early will be assumed to have no treatment effect. These subjects are assumed to copy the profile of placebo group and missing values are imputed based on the distribution estimated from the placebo group under the missing not at random (MNAR) assumption. The rest of missing values in the placebo group and active groups will be imputed using the observed data under the missing at random (MAR) assumption. The multiple imputation model will include factors such as treatment arm and CKD stage in addition to the data outcomes at each visit. Data will be log transformed prior to imputation, and imputed data will be back-transformed in the final imputed data.

The following steps will be performed:

Step 1: Intermittent (non-monotone) missing data will be generated using the MCMC option of SAS PROC MI (using seed=5414). Only the observed hs-CRP measurements will be used to create non-monotone missing data.

Step 2: Subjects in the active group who discontinue early will be imputed under the MNAR assumption. Data in this step will include all early terminated patients from the active groups and all patients from the Placebo group (where data from the Placebo group will be used to inform the MNAR imputation). Patients in the active group, to be imputed under MNAR, will have their post-baseline history removed prior to imputation (only baseline values will be included). MNAR imputation will then be performed for active subjects based on data from patients in the Placebo group.

Step 3: For all other patients, imputation will be performed under the MAR assumption.

For monotone missing data, the values for each pattern will be imputed via the chained equation method using SAS PROC MI option MONOTONE REG ().

These steps will be carried out sequentially to construct 100 hypothetical complete data sets. The final imputed dataset will contain observed and imputed data for baseline and the end of treatment endpoint. End of Treatment endpoint will be calculated by taking the average of observed and imputed values at Week 10 and Week 12. Estimates for ratio to baseline, treatment ratio estimates, 95% confidence intervals, and p-values will be generated from an ANCOVA model (not repeated measures and with no random effects) with log of ratio to baseline as the response variable, variables for chronic kidney stage (stage 3 vs. 4 and 5) and treatment group as categorical fixed effects, and log of baseline value as a covariate. The SAS MIANALYZE procedure will be used to generate estimates, confidence intervals, and p-values. Log transformed estimates will be back-transformed to the original scale in the analysis results.

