6.4.1. Visit 10 (Week 16, Day 113 +6 days)

The following procedures will be performed:

- Record prior/concomitant medications;
- Obtain vital signs;

- Collect sample for chemistry and hematology assessments;
- Collect sample for lipids and subfractions assessment;
- Collect sample for IL-6 (total) assessment;
- Collect sample for hs-CRP assessment;
- Collect Ziltivekimab PK sample;
- Collect ADA sample; and
- Assess AEs.

6.4.2. Visit 11 (Week 20, Day 141 +6 days)/Early Termination Visit for Safety Follow-up Period (ET2)

The following procedures will be performed:

- Record prior/concomitant medications;
- Perform limited physical examination;
- Obtain vital signs prior to ECG recording;
- Perform 12-lead ECG;
- Perform serum pregnancy test for women of childbearing potential only;
- Collect sample for chemistry and hematology assessments;
- Collect sample for IL-6 (total) assessment;
- Collect sample for hs-CRP assessment;
- Collect Ziltivekimab PK sample;
- Collect ADA sample; and
- Assess AEs.

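### Step 2 of the placebo-based multiple imputation removes observed post-baseline hs-CRP of active early terminators, never restores it, and does not define early termination

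*SAP*

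**What the plan says.** SAP 3.4.1, sensitivity analysis (3), is a pattern-mixture analysis on log hs-CRP in the ITT population. Its lead paragraph sets the assumption: "Subjects in the active groups who terminated early will be assumed to have no treatment effect". For these patients, "missing values are imputed based on the distribution estimated from the placebo group".

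The steps that follow are more specific:

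- Step 2 opens with "Subjects in the active group who discontinue early will be imputed under the MNAR assumption". Its input is described as "Data in this step will include all early terminated patients from the active groups and all patients from the Placebo group". The active patients concerned "will have their post-baseline history removed prior to imputation (only baseline values will be included", and are then imputed from placebo.
- Step 3 covers everyone else: "For all other patients, imputation will be performed under the MAR assumption". It mentions no removal of data.
- After the steps have been run in sequence to build 100 completed datasets, "End of Treatment endpoint will be calculated by taking the average of observed and imputed values at Week 10 and Week 12".

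Protocol 9.2.1.2 describes the same analysis with the same no-effect assumption but removes no observed data. SAP section 5 lists no changes from the protocol's analyses.

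Neither document defines early termination for this analysis. The protocol has one early termination visit for the Treatment Period (ET1, at Visit 9) and another at Visit 11: "Early Termination Visit for Safety Follow-up Period (ET2".

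**The concern.** A missing-data sensitivity analysis should fill gaps and leave measured endpoint values alone. Step 2 states a removal rule, applies it to active patients only, and does not make entry depend on a missing Week 10 or Week 12 value. No sentence returns the removed values before End of Treatment is computed. Followed literally, the program discards real endpoint measurements and scores those patients as placebo.

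This is the plan's only missing-not-at-random analysis of the primary endpoint. If it gave a weaker result than the primary analysis, readers would take that as sensitivity to missing data, when part of the shift could come from overwriting data that were observed. The protocol itself (4.5) asks for early termination procedures and follow-up because the drug's pharmacodynamic effect is long, so the discarded values are ones the study set out to collect.

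**Working it through.** **Reading the rule against patient records.** hs-CRP is collected at Week 10 and at Week 12/ET1 (Protocol 6.3.8 and 6.3.9). SAP 3.1.2 assigns early termination results by date when the scheduled visit is unavailable: Days 65 to 78 for Week 10 and Days 79 to 92 for Week 12.

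1. *Active, Week 10 measured, leaves before Week 12 with nothing in the Week 12 window.* This is an early terminator on any definition. Under the lead paragraph, Week 12 is imputed and Week 10 stays. Under Step 2, both come from placebo, so the average of observed and imputed values contains no observed value.
2. *Active, Week 10 measured, leaves during treatment with an ET1 value between Days 79 and 92.* If that value is used as Week 12, nothing is missing. Under Step 2, both values are replaced.
3. *Placebo, either history.* Step 3 applies and the measured values are kept.
4. *Active, Weeks 10 and 12 measured, leaves at Week 16.* The outcome depends on the missing definition. Protocol 4.7 treats the Week 12 visit as primary study completion, which keeps this patient out of Step 2. SAP 3.3.1 counts early discontinuation from the study, and the protocol has ET2, which could bring the patient in.

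**Size of the effect.** The plan gives no figure for this analysis, no dropout rate and no log-scale SD, so what follows is an illustration.

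Inputs:
- 12 patients per arm (SAP 2.2.4).
- Planning difference of -60.74% (SAP 2.2.4). It is a difference in mean percent change. Treating placebo as unchanged and reading it as a ratio gives R = 1 - 0.6074 = 0.3926, with ln R = -0.935. That conversion is an assumption.
- k patients in one active arm whose measured endpoint is wholly overwritten, with k assumed to be 1 to 3.

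Placebo draws have mean log ratio 0, so the expected log treatment ratio is ln R × (12 - k)/12. Each such patient removes 1/12 = 8.3% of it.

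| k | log ratio | ratio | reduction v placebo |
|---|---|---|---|
| 0 | -0.935 | 0.393 | 60.7% |
| 1 | -0.857 | 0.424 | 57.6% |
| 2 | -0.779 | 0.459 | 54.1% |
| 3 | -0.701 | 0.496 | 50.4% |

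For record 1, where only Week 10 was measured, the loss is smaller. With Week 10 kept, the endpoint is roughly (0.3926 + 1)/2 = 0.696, log -0.362. With both imputed it is 1, log 0. The shift is 0.362/12 = 0.030, and 0.030/0.935 is about 3% of the effect. The 8% figure applies to a fully measured endpoint.

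**Simulation check.** One active arm against placebo, placebo-based imputation, ANCOVA on the log ratio with log baseline, Rubin's rules, 30 imputations and 1,500 trials per setting. Mean ratios after overwriting were 0.423 to 0.429, 0.452 to 0.460 and 0.495 to 0.497 for k = 1, 2 and 3, which agrees with the formula. Power of this sensitivity analysis:

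| assumed residual log SD | values kept | k = 1 | k = 2 | k = 3 |
|---|---|---|---|---|
| 0.5 | about 99% | 97% | 90% | 81% |
| 0.8 | about 76% | 65% | 51% | 34% |
| 1.1 | about 49% | 36% | 27% | 16% |

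**The case against.** The best defence is that the removal serves only the imputation model: active-arm history is withheld as a predictor so that imputed values follow the placebo profile, and observed values remain in the final data. Several places support this. SAP 3.1.5 and 3.4 speak of imputing missing data, the lead paragraph says missing values, and the endpoint averages observed and imputed values. The removal applies to patients to be imputed, and a patient with both values has nothing to impute. A merge step could sit in the separate programming specifications that SAP section 6 mentions. This reading is reasonable, so it cannot be said that the analysed dataset will certainly hold overwritten endpoints. It does not close the point: the SAP states the removal and not the retention, and two competent programmers could produce different results.

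A reader might also infer that the SAP orders the overwriting of complete endpoints for patients who leave after Week 12. The documents do not say so. Protocol 4.7 points to Week 12, SAP 3.3.1 and ET2 point to the whole study, and Step 2 invokes neither.

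Different handling by arm is not a fault in itself. It follows from assuming that active early terminators behave like placebo. The fault is limited to measured values.

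The illustration rests on assumed inputs. Three of 12 is a quarter of an arm, and in the earlier single-dose CKD study no subject discontinued (Protocol 1.4.2).

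**Conclusion.** The point stands in this form: Step 2 as written removes observed hs-CRP of active early terminators, has no restore step, and conflicts with the SAP's own wording on missing and observed values and with Protocol 9.2.1.2. The firm case is an active patient who stops during treatment with a measured Week 10 value or an early termination value in the Week 10 or Week 12 window. The safety follow-up case is a possible reading that the undefined term leaves open.

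If values are not restored, the cost is about 8% of the log treatment effect in that arm per fully measured endpoint overwritten, and about 3% where only Week 10 was measured, given 12 per arm, a ratio of 0.393 and an unchanged placebo group. How many patients would be affected cannot be judged from the documents.

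It would be too strong to infer that the trial's main result is at risk. The primary Hodges-Lehmann and Wilcoxon analysis uses no imputation, its error control is unaffected, and the bias runs toward no effect. Severity is minor to moderate.

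**What to change.** Amend Step 2 of SAP 3.4.1 (3) before database lock:

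1. Limit placebo-based imputation to active patients who left before completing Week 12 and have a missing Week 10 and/or Week 12 hs-CRP. This supplies the missing definition.
2. State that post-baseline history is withheld only as a predictor, and that every observed Week 10 or Week 12 value is retained or merged back before End of Treatment is computed, so that only missing values are imputed.
3. State that patients who stop in the Safety Follow-Up Period keep their observed endpoint.

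The cost is a few sentences of SAP text and one merge in the program, with no new data. If retention was always intended, the same text is needed to make that explicit.

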3.4.2 Exploratory Efficacy Endpoints

The exploratory analysis variables measuring change or percent change (as applicable) from baseline to end of treatment will be summarized and analyzed in the same manner as the primary analysis variable (section [3.4.1](#)).

For the continuous efficacy variables, the observed values, change from baseline, and percent change from baseline (as applicable) will be summarized by treatment group using descriptive statistics using ITT population.

For binary endpoints (proportions), proportions of patients and 95% CI for proportions will be based on the normal approximation to binomials. The differences in proportions and 95% CIs for differences for each active group will also be presented.

The sample SAS code for normal approximation of binary endpoints and to calculate differences in proportions and 95% CIs can be found below:

```
*****;  
*Note: ACHIEVE = status of patients achieving endpoint (1 if Yes, 2 if No)  
* TRT = Treatment Group  
*****;  
proc freq data=endpoint;  
by TRT;  
tables ACHIEVE / binomial (Wald exact);  
ods output BinomialCLs=CL BinomialProp=Proportion;  
  
run;  
  
proc freq data=endpoint (where=(trtpn in (#,#));  
table trt*RESPONSE / riskdiff;  
output out=proportion_diff RDIF2 ;  
  
run;
```

The following exploratory efficacy endpoints will be analyzed:

- Difference in the proportion of patients achieving hs-CRP response, defined as hs-CRP < 2.0 mg/L, at End of Treatment (average of Week 10 and Week 12) between each active group and placebo.
- Difference in the percent change in fibrinogen, SAA, NT-pro-BNP, change in hemoglobin and change in albumin from Baseline to End of Treatment (average of Week 10 and Week 12) between each active group and placebo.

- Difference in the percent change in TC, LDL-C, HDL-C, and TG from Baseline to End of Treatment (average of Week 10 and Week 12) between each active group and placebo.

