9.2.1. Analysis of Efficacy

For efficacy (PD) variables, the median difference between each active group and placebo will be analyzed. Efficacy analysis will be performed using the nonparametric Hodges-Lehmann method to estimate median differences between each active group and placebo, associated 95% confidence intervals, and p-values. Additionally, the nonparametric analysis will adjust for the randomization stratification variable CKD Stage (3 vs. 4 and 5)..

For the efficacy variables, the observed values and changes from Baseline will be summarized by treatment group using descriptive statistics and the ITT Population.

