3.1.3 Definition of Baseline

The Baseline value for hs-CRP level will be the average of all hs-CRP values prior to the administration of study drug. The Baseline value of other measures is defined as the last measurement collected prior to the administration of study drug, unless otherwise specified.

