3.4 Efficacy (Pharmacodynamic) Assessment

For all continuous efficacy variables, the number of patients (n), mean, standard deviation (SD), median, quartiles (Q1 and Q3), minimum (min) and maximum (max) values for the observed value, change from baseline, and percent change from baseline will be reported on the ITT population. The difference (Ziltivekimab - Placebo) in percent changes will be presented. For categorical efficacy variables, the number of patients and percentage will be reported on the ITT population.

Due to the known distribution of the primary and secondary efficacy endpoints, normality assumption is usually difficult to satisfy; therefore, a non-parametric approach will be used for the primary and secondary efficacy analysis. Efficacy analysis will be carried out using the Hodges-Lehmann method to estimate median differences and its corresponding 95% confidence intervals for percent change from baseline to end of treatment between each treatment arm vs. Placebo, where end of treatment is the average of assessments at Week 10 and Week 12. The p-value from the Wilcoxon test will also be presented. The nonparametric analysis will account for the covariate CKD Stage (3 vs. 4 and 5) by aligning responses within the strata defined by the covariate prior to analysis.

Sensitivity analyses will be conducted to explore the robustness of the result for primary efficacy endpoint based on mixed models for repeated measures (MMRM) analysis using log of ratio to baseline, and multiple imputation analysis on a log scale. Sensitivity analysis will also be performed based on the PP population using the non-parametric approach. Efficacy data will be summarized by randomized treatment group based on the ITT and PP populations.

The differences in proportions and 95% CIs will be based on the normal approximation to binomials.

Missing data will be imputed only in the context of sensitivity analysis as described in section 3.4.1.

The pharmacodynamic efficacy of two Ziltivekimab doses compared to placebo will be assessed by evaluating the following:

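### The exploratory continuous endpoints are adjusted for CKD stage only; a supportive ANCOVA on the baseline value already collected would add precision unless the marker is very stable

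*SAP*

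**What the plan says.** SAP 3.4.2 gives the continuous exploratory endpoints no method of their own. They "will be summarized and analyzed in the same manner as the primary analysis variable", with a pointer to SAP 3.4.1. The method there is Hodges-Lehmann with a Wilcoxon p-value: "The nonparametric analysis will account for the covariate CKD Stage (3 vs. 4 and 5) by aligning responses within the strata". The sample code in SAP 3.4.1 has CKD stage as the stratum, percent change as the response and no baseline term. Protocol 9.2.1 names the same single adjustment for the efficacy variables.

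Nine continuous markers fall under this rule. Five appear in "Difference in the percent change in fibrinogen, SAA, NT-pro-BNP, change in hemoglobin and change in albumin from Baseline to End of Treatment"; the other four are total cholesterol, LDL-C, HDL-C and triglycerides, all as percent change. Their baseline is a single pre-dose value: "The Baseline value of other measures is defined as the last measurement collected prior to the administration of study drug". Protocol 6.3.1 and Appendix A schedule all nine at Day 1.

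For hs-CRP the SAP goes further. The repeated-measures sensitivity model includes "log of baseline-by-visit interaction as a covariate", and the ANCOVA that follows multiple imputation includes "log of baseline value as a covariate". SAP 3.4 describes these sensitivity analyses as testing the robustness of the primary endpoint result.

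**The concern.** A change score fixes the slope on baseline at 1. If the true slope is lower, which is usual for a marker measured with noise, part of the baseline variation stays in the change score and widens the interval. In any one trial of 12 per arm, a chance difference in baseline also shifts the unadjusted estimate. These are two separate effects, and covariate adjustment deals with both.

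The plan applies that adjustment to hs-CRP, where its own inputs already give power above 99.9% at 12 per arm. It withholds it from the markers for which no power or precision was planned. The SAP's reason for a nonparametric method is non-normality. That is no reason to leave baseline out, and for hs-CRP the SAP already meets the same difficulty with a log-scale model.

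What is at stake is the width of the intervals that describe dose effects on lipids, NT-pro-BNP, fibrinogen, SAA, hemoglobin and albumin.

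**Working it through.** **The plan's own figure.** The only sample-size statement is for hs-CRP (Protocol 9.2.5, SAP 2.2.4): difference 60.74, SD 16.893, two-sided 0.05, 6 per group for 90% power.

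- Normal formula: n = 2 × (1.960 + 1.282)² × (16.893/60.74)² = 1.63, so 2 per group.
- t-test: 3 per group gives 90.1%.
- Exact Wilcoxon, simulated: 4 per group gives about 93%.
- At 6 per group, the t-test power is 99.98%.

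The stated 90% at 6 per group is therefore not reproduced. The discrepancy is conservative and has no bearing on this point. No figure is stated for any exploratory endpoint.

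**Inputs for the precision check.** From the documents: 12 per arm, so N = 24 for each comparison with placebo, and two CKD strata. Assumed: a baseline-to-follow-up correlation rho of 0.3 to 0.9, and equal variances at baseline and follow-up.

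**Formula.** With variance 1 at each time, a change score has variance 2(1 − rho). After regression on baseline the residual variance is 1 − rho². The ratio is (1 + rho)/2. Estimating one more covariate costs a factor 1 + 1/(24 − 3 − 2) = 20/19. Interval width scales with the square root of the product.

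| rho | (1+rho)/2 | × 20/19 | narrowing before the cost | net narrowing |
|---|---|---|---|---|
| 0.3 | 0.65 | 0.684 | 19% | 17% |
| 0.5 | 0.75 | 0.789 | 13% | 11% |
| 0.7 | 0.85 | 0.895 | 8% | 5% |
| 0.8 | 0.90 | 0.947 | 5% | 3% |
| 0.9 | 0.95 | 1.000 | 3% | 0% |

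Break-even is at rho = 2 × 19/20 − 1 = 0.90. A simulation of log-ratio ANCOVA (12 against 12, two strata, lognormal data) agrees: about 17%, 11%, 5%, 2% and 0%.

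**Averaging two visits.** The lipids are scheduled at Week 12 but not Week 10, so under SAP 3.1.2 their End of Treatment is one value and the table applies directly. The other five markers average Weeks 10 and 12. If all visits share one correlation r, the change has variance 1.5(1 − r), the residual is (1 − r)(1 + 2r)/2, and the ratio is (1 + 2r)/3. Net narrowing is then about 16%, 8%, 4-5% and 1% at r = 0.5, 0.7, 0.8 and 0.9. If Weeks 10 and 12 correlate more closely with each other than with baseline, the gain lies between the two sets of figures.

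**Power and type I error.** Simulation at 12 against 12, two strata, lognormal data, true effect 1.2 SD of the log change, over two percent-change settings and one change-score setting:

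| rho | planned test | baseline-adjusted rank tests | log ANCOVA |
|---|---|---|---|
| 0.3 | 76-77% | 86-91% | 91-92% |
| 0.5 | 76-78% | 83-86% | 88-89% |
| 0.7 | 76-77% | 79-81% | 83% |
| 0.8 | 77-78% | 78-80% | 81-83% |
| 0.9 | 78% | 76-78% | 80-81% |

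The log ANCOVA column flatters the fix a little, because the data were generated to suit that model. Its gain of about 2 to 3 points at rho 0.9 comes from the parametric form and not from baseline. Under no effect, every method rejected in about 4% to 6% of 2,000 runs (standard error √(0.05 × 0.95/2000) = 0.5 points).

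**The case against.** The strongest reply is that this is a preference and not a defect. The endpoints are exploratory, sit outside the sequential test and carry no power claim. Change and percent change already use baseline, and the planned test holds its error rate. All of this stands, and it sets the weight of the point. It does not show that the adjustment is worthless: unless a marker is very stable, precision is lost that costs almost nothing to recover.

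A second reply is that the pointer to SAP 3.4.1 takes in the whole section, including the two baseline-adjusted models. The wording allows that. SAP 3.4, however, ties the sensitivity analyses to the primary endpoint, so the narrower reading is the better supported one. One sentence would settle it.

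A third concerns the remedy. A rank ANCOVA gives a p-value but no interval on the marker's scale, so it would not narrow what is reported. Demoting Hodges-Lehmann to a descriptive role would depart from Protocol 9.2.1, while SAP section 5 records no changes. Both objections are right, and the fix below is an added model that leaves the planned analysis in place.

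A reader might also infer that LDL-C and triglycerides are the harm question this trial must answer, citing Protocol 1.5. That section gives the question of dose against lipid increases to a separate ongoing Phase 2 study. Here the lipids are exploratory markers of atherosclerosis risk (Protocol 2.4).

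**Conclusion.** The point holds as a modest matter of efficiency. For the nine continuous exploratory markers, CKD stage is the only adjustment, and a baseline value already collected is not used as a covariate.

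Net of the small-sample cost, adjustment narrows the interval by about 17%, 11%, 5%, 2-3% and 0% at correlations of 0.3, 0.5, 0.7, 0.8 and 0.9. These figures rest on assumed correlations, equal variances, 12 per arm and no dropout. The documents state no correlation for any marker, so the actual gain cannot be placed within that range.

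Three stronger readings are not supported:

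- **The planned test is invalid.** Its simulated type I error is near 5%.
- **Power rises by at least 5 points for any correlation up to about 0.7.** At 0.7 the simulated gain of the rank tests is roughly 2 to 5 points, and at 0.9 there is none.
- **The primary conclusion is affected.** On the stated inputs hs-CRP has power to spare, and its sensitivity models already adjust for baseline.

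The hs-CRP responder proportion has its own normal-approximation analysis and is not covered here.

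**What to change.** Keep the Hodges-Lehmann/Wilcoxon analysis as planned. Before unblinding, add to SAP 3.4.2 a supportive ANCOVA with treatment, CKD stage (3 vs 4 and 5) and baseline:

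- **Fibrinogen, SAA, NT-pro-BNP and the four lipids:** log ratio to baseline as the response, log baseline as the covariate, results back-transformed to ratios against placebo with 95% intervals.
- **Hemoglobin and albumin:** change as the response, untransformed baseline as the covariate, because their endpoint is change.

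State in the same paragraph that the pointer to SAP 3.4.1 means the primary method and not its sensitivity models. List the ANCOVA in SAP section 5 as an addition to the protocol analysis.

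The log-ratio model form is already written in SAP 3.4.1 for hs-CRP, so the cost is a short paragraph and minor programming, with no new data. The downsides are one more model output per endpoint, a parametric assumption in the supportive analysis, and little gain for very stable markers. The benefit beyond precision is that any chance baseline imbalance at 12 per arm would be handled by a pre-specified analysis and not by one chosen afterwards.
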